## Section 9.9 Data Safety Monitoring Board or Plan

## 9.9) Provide a Data Safety Monitoring Plan (DSMP) or the details of a Data Safety Monitoring Board; if a written plan is available, attach a copy of the plan to the submission form.

The study is a pilot intervention that will randomize 32 participants with PTSD to either yoga plus Mantram repetition or to a relaxation comparison group. Study investigators will review all adverse events on a weekly basis and report them as appropriate to the IRB according to established requirements. Drs.[name] and [name] have clinical and research expertise with PTSD. If the rate of serious adverse events attributed to either intervention results in an imbalanced SEA rate between the two study arms, or is higher than clinically expected, the study will be stopped to assess safety. If adjustments to the intervention to remedy the problem are not obvious or easily made, the study intervention(s) will be discontinued.

Research activities will cease if any participant or study staff member that had recent study interactions with study staff or other participants tests positive for COVID-19 within 3 weeks of those interactions. All at risk persons will be notified of their risk at that time.

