**C11.2. Data Analysis and Feasibility Criteria.** Recruitment rates will be compared to the specified goal of a mean of 4 enrolled participants per month. We expect to need 5 screened eligible participants per month because some fail to follow through and enroll. If rates remain below 50% of the goal, feasibility will not be established for a full-scale RCT. Attendance rates in many mind-body intervention studies range between 50-80%. For this study, attendance of 50% or higher will be required to support further research on either intervention. A retention rate of 80% or higher is considered an adequate retention rate at a post-intervention assessment for an RCT. Thus, we will use a slightly more lenient 75% or higher retention to indicate feasibility to proceed. Participant satisfaction rates of 75% or higher (measured as % of participants checking agree or strongly agree) will be used to indicate acceptability of the interventions, with little or no modifications needed prior to a larger study. AEs will be evaluated in collaboration with the VASD IRB and the DSMC. In general, any more than 1-2 serious AEs attributed to either intervention among the 20 participants assigned to each would give cause for pausing the intervention until obvious solutions and modifications were identified. Mean time to complete the questionnaires is estimated at 40 minutes. Mean time of 80 minutes or more would indicate burden issues and review of the battery and/or compensation level. Instructor fidelity of under 75% will indicate a need for retraining and/or clarifications of the instructor manual. Finally, mean changes on outcome measures will be compared to minimum clinically important differences where established.

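### The serious-AE rules in Section 9 (C11.2) and Section 9.9 differ in trigger, scope and named reviewers, and no text says which governs

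*Combined protocol and SAP*

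**What the plan says.** Section 9, C11.2 (Data Analysis and Feasibility Criteria) first says that "AEs will be evaluated in collaboration with the VASD IRB and the DSMC". As a general guide it then says that "any more than 1-2 serious AEs attributed to either intervention", out of 20 people per arm, "would give cause for pausing the intervention until obvious solutions and modifications were identified".

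Section 9.9 is the data safety monitoring plan. It begins: "Study investigators will review all adverse events on a weekly basis", with reporting to the IRB as appropriate. Its rule is that if the attributed serious-AE rate "results in an imbalanced SEA rate between the two study arms, or is higher than clinically expected, the study will be stopped"; the purpose given for the stop is a safety assessment. The next step is conditional: "If adjustments to the intervention to remedy the problem are not obvious or easily made, the study intervention(s) will be discontinued".

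Three other places bear on the point:

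- Section 9.8, C9.3 says that a DSMC will be set up at the start of the study. Section 9.9 does not mention it.
- Section 9, C7 describes expected AEs in words only: very few in yoga trials, and none attributed to mantram repetition.
- The form for Section 15 asks, where applicable, for the conditions that trigger an immediate suspension. The answer gives none for serious AEs.

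**The concern.** Both passages are current, both address serious AEs attributed to an intervention, and neither refers to the other. One counts events within an intervention. The other compares arms, or compares a rate with an expectation that is never stated. One pauses *the intervention*; the other stops *the study*. One names the IRB and the DSMC; the other names the investigators and the IRB.

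The same event can therefore call for different responses depending on which section is consulted. Two things are at stake. Participant protection should not depend on how an undefined word is read after an event has happened. Safety is also one of the conditions for proposing the full-scale trial (Section 9, C1 and C1.2), so the safety conclusion should rest on a rule that was fixed beforehand.

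**Working it through.** **1. The plan's own figure.** C11.2 uses 20 participants per arm. The total randomized is 32 (Sections 2a, 6, 9 C1.2 and 9.9), and 32 / 2 = 16. Section 9, C9 gives 8 per intervention in each of two cohorts, and 8 × 2 = 16. Twenty per arm would need 20 × 2 = 40. The figure of 20 does not follow from the stated sample size.

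**2. The rules side by side.**

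| | Section 9, C11.2 | Section 9.9 |
|---|---|---|
| Trigger | More than 1-2 attributed events in an intervention (second or third event) | Attributed rate imbalanced between arms, or higher than clinically expected; no figure for either |
| Scope | Pause the intervention | Stop the study to assess safety; discontinue intervention(s) if there is no easy remedy |
| Named reviewers | IRB and DSMC | Investigators and IRB |
| Force | General guide; cause for pausing | Will be stopped |

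**3. Test cases, 16 per arm, with imbalanced read literally as unequal rates.**

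- 1 v 0: 1/16 = 6.25% v 0%. The Section 9.9 imbalance limb is met. C11.2 is not met on either reading of 1-2.
- 2 v 0: 2/16 = 12.5% v 0%. Section 9.9 is met. C11.2 is met only if 1-2 means more than 1.
- 3 v 3: 3/16 = 18.75% in each arm. C11.2 is met. The imbalance limb is not, but the limb on clinical expectation could be.

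**4. How much the undefined word matters.** Suppose, as an assumption, that imbalanced meant a two-sided Fisher p below 0.05. For x v 0 with 16 per arm, p = 2 × C(16,x) / C(32,x).

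- x = 1: 2 × 16 / 32 = 1.00
- x = 4: 2 × 1,820 / 35,960 = 0.101
- x = 5: 2 × 4,368 / 201,376 = 0.043

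The trigger against an arm with no events would then be 5 v 0 instead of 1 v 0.

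**5. How often the triggers part.** Let X and Y be independent Binomial(16, p) counts with the same p in both arms. The values of p are assumptions. With b(k) the binomial probability and F its cumulative sum:

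- Unequal counts: 1 − Σ b(k)²
- C11.2 met in at least one arm: 1 − F(1)² for more than 1; 1 − F(2)² for more than 2

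At p = 2%, b(0) = 0.7238, b(1) = 0.2363, b(2) = 0.0362 and b(3) = 0.0034. The squares sum to 0.5239 + 0.0559 + 0.0013 + 0.0000 = 0.5811, so unequal counts have probability 0.419. F(1) = 0.96014 gives 0.078, and F(2) = 0.99631 gives 0.007.

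| Assumed p | Unequal counts | C11.2, more than 1 | C11.2, more than 2 | Unequal, C11.2 (more than 1) not met | Unequal, C11.2 (more than 2) not met |
|---|---|---|---|---|---|
| 1% | 25.6% | 2.2% | 0.1% | 23.4% | 25.5% |
| 2% | 41.9% | 7.8% | 0.7% | 34.2% | 41.2% |
| 5% | 64.6% | 34.3% | 8.4% | 32.6% | 56.4% |

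With 20 per arm instead, unequal counts have probability 30%, 48% and 69%. The C11.2 trigger has probability 3%, 12% and 46% (more than 1) or 0.2%, 1.4% and 15% (more than 2). The pattern does not depend on the denominator.

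These are end-of-study counts. Under weekly review a final 1 v 1 would usually have passed through 1 v 0. The literal imbalance limb could then be met whenever any event occurs, with probability at most 1 − (1 − p)³²: 27.5%, 47.6% and 80.6%.

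**The case against.** A reader might infer more than the text supports: that a single attributed serious AE stops the whole study under Section 9.9 and triggers nothing under C11.2. Neither half stands as written.

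- Section 9.9 sets no margin for imbalance, so a stop at 1 v 0 is its literal reading and not a stated rule.
- *Nothing* is wrong for C11.2. AEs are evaluated with the IRB and DSMC whatever the count, and Section 9.9 adds weekly review. C11.2 is also worded as a general guide and does not forbid action at one event.
- The Section 9.9 stop is for assessment, and discontinuation comes later and conditionally. C11.2 likewise halts, looks for a solution and modifies. In action, the real difference is scope.
- The 3 v 3 case does not prove that the rules part in the other direction. Three of 16 in each arm could well be higher than clinically expected, given C7.
- It does not follow that staff could comply by choosing either rule. Section 9.9 is worded as mandatory, and both rules can be applied together.
- Section 9.9 omits the DSMC but does not exclude it, and its form allows a separate written plan to be attached, which was not available for this review.

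The probabilities also depend on assumed risks. If attributed events are rarer, as C7 suggests, unequal counts fall to about 14% at 0.5% and 3% at 0.1%.

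All of this limits the wording and the size. It does not remove the conflict: different triggers, different scope, different named reviewers, three undefined terms (*1-2*, *imbalanced*, *clinically expected*), and no order of precedence.

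**Conclusion.** The concern holds as an unreconciled pair of rules. On the literal reading of imbalanced, the first attributed event with none in the other arm meets Section 9.9 and stays below the C11.2 pause threshold, while still being reviewed. On a significance-test reading, Section 9.9 would not act until 5 v 0. That spread, from one event to five, is itself part of the defect.

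The size rests on three assumptions: 16 per arm, equal and independent attributed risk of 1-5%, and the literal reading. On these, unequal counts have probability 26-65%, against 2-34% or 0.1-8% for the C11.2 trigger, depending on what 1-2 means. The denominator error needs no assumption: 20 per arm does not match 32 randomized.

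The documents do not support a claim that attendance, retention or outcome data would be lost, because no text says that assessments cease during a stop. They also give no basis here for preferring one rule to the other.

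**What to change.** The sponsor and the DSMC should reconcile C11.2 and Section 9.9 into one consistent rule and use it in both places. The reconciled text should settle:

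- the trigger, including what 1-2, imbalanced and clinically expected mean wherever those terms are kept;
- the scope, that is, the intervention or the study;
- the reviewing body, with the role of the DSMC described in the same way in C11.2, C9.3 and Section 9.9.

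The denominator of 20 per arm in C11.2 should be corrected to match the 32 randomized. Which trigger and action to keep is for the sponsor and the DSMC to decide.

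The cost is protocol wording, mainly in two sections, and one amendment through the DSMC and IRB. No procedures are added.

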## Section 9.11 Pictures and Audio/Video Recordings of Patients

**9.11) Describe the purpose of photographs (facial), or audio, or video recordings of patients. Describe whether the recordings will contain, or potentially contain, identifiers. Note: use of photographs or recordings must be covered in the informed consent process and documented consent documents (e.g., consent form, information sheets, telephone screen scripts).**

Qualitative interviews will be audio-recorded so that they can be professionally transcribed before being analyzed. This is necessary to conduct high quality research.

The yoga and mantram interventions will be video-recorded to assess instructor fidelity. The camera is fixed and focused on the instructor, but may show the back or part of the participants, and may be identifiable.

## Section 10 - Human Subjects

**10) Describe the characteristics of the proposed subject population. Include age, gender, ethnicity, and health status as appropriate. Note: Data about people are still considered “human subjects” by the IRB, so even if you do not intend to contact the patients whose charts you will review, you still describe the characteristics related to the subjects whose charts you will review.**

- Provide inclusion and exclusion criteria as appropriate. Provide a statement how non pregnancy is confirmed if pregnancy is an exclusion criteria.
- For multisite studies, provide the total number of subjects from all sites and include description of the local site's role as a coordinating center if applicable.
- Indicate the number of VA participants to be studied.
- Indicate the estimated number of consented subjects that will fail the screening process, if any.

Human Subjects Involvement and Characteristics. The study will recruit 32 patients from the VA San Diego Healthcare System with a diagnosis of PTSD, and a diagnosis of chronic low back pain (cLBP) and/or chronic neck pain (cNP).

Inclusion Criteria: age > 18, PTSD Checklist (PCL-5) score of  $\geq 25$ , score of  $\geq 25$  on Montreal Cognitive Assessment (MoCA), willing to reduce or cease opioid medications, willing to attend 12-weeks of yoga and complete 3 assessments.

Exclusion Criteria: serious or unstable psychiatric illness (e.g. psychosis, mania), suicidal or homicidal ideation WITH active plan and/or intent, < 3 months since major trauma event, moderate or severe cognitive impairment, practiced yoga  $> 2x$  in the last 6 months, coexisting medical illness with yoga contraindicated.

### Screening Measures

Medical History Interview. All participants will complete a standard interview regarding medical history and functioning. In addition, a chart review of the VA patient record will be conducted to assess medical status.

C3.3. The PCL-5 is a 20-item self-report measure assessing 20 DSM-5 symptoms of PTSD. It has been validated in Veterans.

C3.4. MoCA is a brief screen for cognitive impairment. We will include those with a score of  $\geq 25$ , based on the Youdon index to be inclusive, yet ensure that participants are able to understand the informed consent document, their rights as a participant, the assessments, and the intervention instructions.

C3.5. Columbia Suicide Severity Rating Scale. Participants will be asked about suicidal thoughts, plan, intent, and behavior, as well as assessment of risk and protective factors.

Based on data from a previous study, only about 25% or less failed the screening exam. Thus we expected to screen about 44 patients and that 12 or less will fail screening.

Qualitative Interviews (QI) will be conducted with a subset 12 of the 32 participants recruited using the criteria above. Participants will be invited to participate in the QI if they had challenges attending, asked to withdraw from the study, or if they have low satisfaction with the program. However, we will also interview at least 4 participants who attended well and were satisfied with the interventions and study.

#### Inclusion of Women and Minorities

Women and minorities will be included in this study. The nature of the research does not pertain specifically to either women or minorities but we will encourage their participation as much as possible in order to generalize results where possible. Less than 10% of VA patients served at the VASDHS are women, but pilot data from the VA San Diego and other non-VA studies suggest that women may be more receptive to yoga and/or MR interventions and may be overrepresented as a proportion of VA patients. Thus, we will have a recruitment target of 20% women. Ethnic minorities were also well represented in our previous VA yoga and MR studies. We will have a target of recruiting at least 30% racial or ethnic minorities for this study.

Children will not be recruited since they are not patients at the VA San Diego.

## Section 10.2 Pregnant Women

### 10.2a) Are pregnant women the focus of the research?

Yes  No

### 10.2b) Provide the justification for including pregnant women and address any special risks, protections, and safeguards.

VA patients with PTSD who are women and are pregnant still require treatment of their chronic pain. Pregnant women who qualify on all other aspects of the study will be allowed to participate in yoga if their primary care physician provides written approval.

## Section 10.6 Avoiding coercion of students or employees

### 10.6) Indicate how coercion of students and/or employees will be avoided:

Many VA patients are also VA employees. Their status as students or employees will in general not be known to study staff. The voluntary nature of participation will be emphasized in the informed consent process and throughout the study. Students or employees will not be targeted in any way. They may respond to flyers or be told about the study by clinicians in their role as patients. If it becomes known to study staff that an enrolled participant or an individual considering participation is a student or employee, they will be told that participation or non-participation will not affect their student or employee status in any way.

## Section 11 - Recruitment

### 11) Describe, step-by-step, the plans for recruitment of subjects (or selection of subjects as in record review).

**This description must include how, when, and where potential subjects are approached as well as procedures for identifying potential participants (through medical records, physician referral, third-party sources, etc.). Include how selection is equitable. Indicate if vulnerability to coercion may be present and if so plans to ensure voluntary participation.**

Recruitment will occur through flyers posted through VA medical centers, and through clinical providers. Clinical providers will be briefed on the study goals and procedures, risks, and potential benefits. During the enrollment period, clinical providers will personally invite and refer patients to participate, and when appropriate, direct patients to speak with study research staff, who will be available during clinics. Patients who speak with research staff will be given a clear description of all aspects of study participation, including randomization, collection of electronic data, and incentives. Those who wish to enroll and meet entry criteria above by self-report will undergo signed informed consent, after which electronic medical records will be reviewed to confirm, document, and record eligibility criteria.

## Section 11.1 Recruitment Materials

**11.1) Identify all recruitment materials (flyers, advertisements, letters, etc.) that will be used; include the web address for any web-based advertisements. The text of all communications with prospective participants must be reviewed and approved by the IRB before it can be used. You will be reminded to attach copies of recruitment materials to the initial submission packet. Note: *Posting of flyers with pull tabs is not permitted within VASDHS (including the VMRF building). However, you may request to advertise on the e-boards (located at the elevators and throughout the facility) or on the VASDHS Research Opportunities web-page.***

Flyers, posting on monitors in waiting rooms.

## Section 12 - Informed Consent

**12) Indicate whether or not each category of consent is involved in this study:**

12a) Will the study team obtain information or biospecimens for the purpose of screening, recruiting, or determining the eligibility of prospective subjects without (or prior to) obtaining informed consent of the prospective subject or the prospective subject's LAR?

Yes  No

12b) **Signed** informed consent

Yes  No

12c) Waiver of documented consent (e.g., **oral** consent) for all or part of the study.

Yes  No

12d) Request for a **waiver** of consent for all or some study activities.

Yes  No

12e) Alteration of **other required elements** of consent.

Yes  No

12f) **Child** assent to participate (Director approval will be required)

Yes  No

12g) Will any language **other than English** be used by those obtaining consent and understood by the prospective participant or the legally authorized representative?

Yes  No

12h) **Decisional Capacity Assessment** to determine if participants have the capacity to consent for themselves.

Yes  No

12i) Surrogate consent (legally authorized representative)

Yes  No

## Section 12.1 Informed Consent Process

12.1a) Will consent be obtained before any study procedures are performed (including screening procedures except screening procedures with Consent and/or HIPAA waiver when required)?

Yes  No

12.1b) Will the information being communicated to the participant or legally authorized representative during the consent process include exculpatory language through which the participant or legally authorized representative is made to waive or appear to waive any of the participant's legal rights or release or appear to release the Researcher, Sponsor, the VA or its agents from liability for negligence.

Yes  No

12.1c) A master list of all VA subjects consented (written or not) under this protocol will be maintained.

Agree  Disagree

12.1d) Identify the circumstances under which consent will be obtained including where the process will take place; any waiting period between describing the research and obtaining consent including sufficient time for the prospective participant to consider participation, and any steps taken to minimize the possibility of coercion or undue influence.

The study coordinator or research staff will describe the study, requirements of participation, and inclusion/exclusion criteria via telephone for any prospective participants that inquire. If they remain interested, they will be scheduled for the informed consent process at a mutually available time, either in-person or through an online process described below. They will be allowed to have another person present if they would like. The consent form and study procedures will be fully explained at the appointment. The voluntary nature of participation will be emphasized. They will be given additional time to make a decision as needed.

For remote online consenting, we will use traditional mail or encrypted Azure email to send prospective participants a packet containing: 1) the approved Informed Consent and HIPAA document; 2) the CA Experimental Subjects Bill of Rights, and 3) the COVID-19 consent addendum. We will then arrange an appointment that will use Veteran Video Connect to complete the informed consent process, explain the HIPAA Authorization, the COVID-19 addendum, in-person procedures, and CA Experimental Subjects Bill of Rights. The staff member will witness the signing of the forms and will instruct the participant to provide documentation of written informed consent by taking a screenshot while they hold up the signed forms to the camera (approval date and signature must be clearly visible). These electronic documents will be stored electronically separate from study data in the PI's study folder on the R: drive, and the participant will retain their copies.

## Section 12.6 Decisional Capacity Assessment

12.6a) Describe the method(s) for determination of decisional capacity: (see ? for guidance) *Please note that documentation of the assessment is required.*

Decisional capacity will be assessed with the Montreal Cognitive Assessment (MoCA), which is a brief screen for cognitive impairment. We will include those with a score of  $\geq 25$ , based on the Youdon index to ensure that participants are able to understand the informed consent document, their rights as a participant, the assessments, and the intervention instructions.

12.6b) If subjects with limited decisional capacity will be enrolled, describe methods for obtaining subject

